COVER PAGE – STUDY PROTOCOL

Title: Cranial electrotherapy stimulation: Piloting a road to PTSD prevention in first responders

NCT number: NCT06203717

Document date: 08/15/2024

BUTLER HOSPITAL
INSTITUTIONAL REVIEW BOARD
PROTOCOL

Project**Title of Project:** Cranial electrotherapy stimulation: Piloting a road to PTSD prevention in first responders**Short Title of Project:** CES in firefighters**Principal Investigator (PI):** [REDACTED]**Other Investigator(s):** [REDACTED]**Revision History:**

Version Number	Version Date	Summary of Revisions
1.0	08/28/2023	First version submitted
	09/18/2023	First version approved
2.0	12/14/2023	
 1. Changed PI from [REDACTED]. 2. Added [REDACTED] as co-investigator to the study team. 3. Corrected error in ecological momentary assessment (EMA). 4. Added new advertisement material.
3.0	05/28/2024	
 1. Revised CNE Research Application to change Device Risk Level to "nonsignificant risk device" instead of "N/A". 2. Updated protocol to include XNAT – a password protected secure server – for transfer of MRI data from MRF to Butler. 3. Broadening of recruitment locations to include community locations (e.g. coffee shops).
4.0	8/15/24	
 1. Broadening of recruitment methods through social media marketing. 2. Update protocol to allow for texting for initial outreach to potential participants.

Description of Study**A. Specific Aims**

Aim 1: Test the feasibility and acceptability of Cranial electrotherapy stimulation (CES) in firefighter first responders.

Prediction: CES is feasible quantified as more than 75% of sessions completed, and acceptable quantified as less than 20% attrition in the sample, such that at least 16 out of 20 firefighters complete, for example, at least 15 out of 20 sessions over the course of four weeks.

Aim 2: Test the effects of CES on subjective homeostatic functioning in firefighter first responders.

Prediction: CES will reduce subjective fatigue and frequency and intensity of negative emotions (e.g., distressed, nervous) while increasing the experience of positive emotions (e.g., calm, inspired) assessed naturalistically in near real-time through ecological momentary assessments (EMA).

Aim 3: Test the effect of CES on objective homeostatic functioning in firefighter first responders.

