Critical Gaps in Knowledge. Despite CES' potential for use in first responders, there are no studies that evaluate if a predefined four-week course of CES is feasible and acceptable in firefighters. Although one study examined CES in a sample of 86 first responders consisting mainly of law enforcement as well as 10 firefighters, participants were "permitted to use the device any time of day and for any indication" [c.f. 17] and the report does not mention of how often, at what time of day, and for how long participants used the device or whether

there were difficulties with its use, providing no information about feasibility or acceptability. This is important because it is advised to avoid the use of heavy machinery after CES. Therefore, the application of CES should be carefully integrated with the firefighter work schedules, starting with its use only on off-duty days.

Additionally, there are no studies that test the effects of CES on subjective and objective indices of homeostatic functioning in active-duty firefighters to gain insight into possible mechanisms of CES-modulatory effects. In fact, despite a literature on effectiveness for anxiety, insomnia, and depression [but see 18 for a negative randomized controlled trial], the mechanism of CES effects on homeostatic functioning remains rather hypothetical with little direct evidence [19].

Here we propose to address these critical gaps in science by testing if a course of four weeks of CES in firefighters is 1) feasible and acceptable in this population; 2) impacts subjective variables associated with homeostasis, including fatigue, frequency and intensity of negative and positive emotions (i.e., distressed, nervous, calm, inspired); and 3) changes objective variables associated with homeostasis, including functional and structural neural connectivity, heart rate variability, and sleep quality in a subset of participants.

C. Experimental Method

C1. Brief Description of Subjects

Participants will be 20 active-duty firefighters in the State of Rhode Island, between 18-56 years old.

Participants will be of any racial or ethnic group and of any gender.

C2. Study Design

This study will use a within-subject design, with all participants completing all experimental procedures with no difference to how CES will be applied. Recruitment of 20 participants incorporates an estimated 20% attrition to allow data collection on 16 participants.

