The Project Leaders of this supplement, [REDACTED] will be responsible for and supervise data collection and data management. The main goals of this study involve assessing feasibility (i.e., > 75% of CES sessions completed) and acceptability (i.e., < 20% attrition in the sample) of a 4-week course of CES in active-duty firefighters (i.e., at least 16 out of 20 firefighters complete at least 15 out of 20 sessions over four weeks) and obtaining preliminary signal of effect to inform the design of a future, collaborative clinical trial to test efficacy of CES for the prevention of PTSD in first responders. Our primary outcome measures include the number of completed sessions to quantify feasibility and attrition in the sample assessing acceptability (Aim 1). In addition, we will collect data on subjective fatigue, negative and positive emotions using ecological momentary assessment (Aim 2) as well as heart rate variability and sleep quality (Aim 3). Finally, we will collect pre- and post-CES data on clinical symptoms (PTSD, depression, anxiety) and MRI-based resting state functional connectivity and structural connectivity (Aim 3). Given the preliminary nature, the proposed study is not designed to have adequate power to robustly test whether CES is effective for PTSD prevention, which would constitute the long-term goal of the proposed work. As such the proposed number of 20 individuals is solely meant to achieve the listed aims.

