Care New England's instance of REDCap is hosted within the Care New England data center in Warwick, RI. This REDCap instance is role-based and is fully integrated with CNE's Active Directory structure. It enjoys 24/7/365 enterprise-level support and security inherit to CNE's HIPAA-compliant data center. Network transmissions (data entry, survey submission, and web browsing) to and from REDCap are protected via TLS 1.2 encryption. REDCap's data is stored on encrypted servers within CNE's data center. The REDCap Consortium is composed of thousands of active institutional partners in over one hundred countries who utilize and support REDCap. REDCap was developed specifically around HIPAA-Security guidelines, and more information about the consortium and system security can be found at <http://www.projectredcap.org/>.

De-identified MRI scans will be transferred from the computer in the scanner room at the MRF to XNAT - a password protected secure server – instituted by the MRF for secure transfer of MRI data.

D. Material Inducements

A total of up to \$304 in compensation will be offered for the study-related procedures administered in this study. Participants will be compensated with \$50 for completing Visit 1, \$40 for each MRI session (Visit 2 and 3), and \$50 for completing Visit 4. This totals \$180 in compensation for study visits. In addition, participants will be compensated with \$2 per CES session they complete (max 20 sessions; \$40) and \$2 for each EMA survey they complete, plus a weekly \$5 bonus when they complete 6 out of 7 daily surveys each week (>85% EMA completion compliance, 4 weeks: 28 daily surveys (\$2*28=\$56) plus four weekly surveys (\$2*4=\$8) plus \$5 weekly bonus (\$5*4=\$20) totaling to \$84). Thus, participants can earn another \$124 if they complete all EMA surveys and all CES sessions.

Compensation will be in the form of checks or gift cards, and will be provided after each Study Visit. If participants opt for compensation through checks, we will need to collect additional sensitive data (e.g., participant home address).

E. Training of Research Personnel

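### The lowest counts that pass Aim 1 (15 of 20 sessions, 16 of 20 firefighters) fail the strict percentages they are meant to restate

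*Combined protocol and SAP*

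**What the plan says.** Section A (Aim 1) defines feasible and acceptable as "more than 75% of sessions completed, and acceptable quantified as less than 20% attrition in the sample". It then spells this out as "at least 16 out of 20 firefighters complete, for example, at least 15 out of 20 sessions".

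Section C4 (Data Analysis) repeats the percentages as "feasibility (i.e., > 75% of CES sessions completed) and acceptability (i.e., < 20% attrition in the sample". In the same sentence it restates them, introduced by i.e. and with no qualifier, as "at least 16 out of 20 firefighters complete at least 15 out of 20 sessions over four weeks".

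Section C4 also gives these criteria their status: "Our primary outcome measures include the number of completed sessions to quantify feasibility and attrition in the sample assessing acceptability".

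Two other sections supply the denominators. Section C2 (Study Design) says "Recruitment of 20 participants incorporates an estimated 20% attrition to allow data collection on 16 participants". Section D (Material Inducements) pays participants "per CES session they complete (max 20 sessions", which confirms 20 as the session maximum.

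**The concern.** Each criterion appears twice, once as a strict percentage and once as an inclusive count, and the document presents the two as the same thing. They differ at the boundary. A firefighter with exactly 15 sessions counts under one form and not under the other. A sample that loses exactly four people meets the retention part of the count and fails the attrition percentage.

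These are the primary outcome measures. If the results fall on the boundary, whether the report says CES was feasible and acceptable depends on which form is applied, and nothing in the document settles that beforehand. The retention boundary is also the outcome that section C2 allows for.

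A related gap is that the document does not say whether the 75% is judged for each participant or pooled over all sessions. The count form implies per participant.

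**Working it through.** **Inputs.** More than 75% of sessions and less than 20% attrition (sections A and C4); at least 15 of 20 sessions and at least 16 of 20 firefighters (sections A and C4); 20 recruited, 20% estimated attrition, 16 with data (section C2); maximum 20 sessions (section D).

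**Reproducing the plan's figures.** 20 × (1 − 0.20) = 16, which is the figure in section C2. 0.75 × 20 = 15. So the stated counts follow if the criteria are read as at least 75% and at most 20%.

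**Testing the counts against the strict criteria.**

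- Sessions: 15/20 = 0.75, which is not above 0.75. The smallest k with k/20 > 0.75 is 16 (16/20 = 0.80).
- Retention: with 16 retained, attrition is 4/20 = 0.20, which is not below 0.20. The smallest m with (20 − m)/20 < 0.20 is 17 (3/20 = 0.15).

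Both strict criteria therefore need one unit more than the stated count.

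**How often the retention boundary matters.** The document gives only the estimated 20% attrition; the other retention rates below are assumptions. Let X be the number retained and suppose X ~ Binomial(20, r), with participants independent. The count needs X ≥ 16, the percentage needs X ≥ 17, and they disagree when X = 16, with probability C(20,16) × r^16 × (1 − r)^4. At r = 0.80 this is 4845 × 0.80^16 × 0.20^4 = 0.218.

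| True retention r | P(X ≥ 16) | P(X ≥ 17) | P(X = 16) |
|---|---|---|---|
| 75% | 41.5% | 22.5% | 19.0% |
| 80% (planned) | 63.0% | 41.1% | 21.8% |
| 85% | 83.0% | 64.8% | 18.2% |
| 90% | 95.7% | 86.7% | 9.0% |

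**The full count rule.** As worded, it is joint: the 16 firefighters must also each reach 15 sessions. So 63.0% is an upper bound for passing it at 80% retention. If 95% of those retained reach 15 sessions (assumed), the per-person probability is 0.80 × 0.95 = 0.76 and P(≥ 16 of 20) = 45.6%. If 90% do (assumed), it is 0.80 × 0.90 = 0.72 and 30.2%. These two figures show what the joint rule demands; they do not measure the gap between the two forms.

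**Does a pooled reading reconcile the forms?** No.

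- Sixteen firefighters at 15 sessions each give 16 × 15 = 240 sessions. Among those retained that is 240/320 = 75.0%, still not above 75%.
- Over all enrolled, if the four dropouts did no sessions (assumed), it is 240/400 = 60%.
- Even the stricter counts give 17 × 16 = 272 and 272/400 = 68% if three dropouts did none.

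**The case against.** The arithmetic is not in dispute; the case against is about scope and weight.

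- **Only the minimum of each count fails.** Anyone with 16 to 20 sessions, or a sample with 17 to 20 retained, satisfies both forms. This is correct, and the conflict is confined to the boundary.
- **Aim 1 marks the session count as an example.** It does, and that softens the session half there. It does not touch the 16-of-20 count, and section C4 gives both counts without a qualifier.
- **The session conflict depends on the per-participant reading.** Pooled over retained firefighters who all reach 15, the forms conflict only if every one stops at exactly 15. That is fair, but the document does not adopt the pooled reading and its counts point the other way.
- **The count is a joint rule.** With four dropouts it passes only if all 16 who remain reach 15 sessions. This also stands, which is why the table covers the retention part alone.
- **The probabilities rest on assumed retention.** They do, apart from the planned 80%. At 95% retention the disagreement falls to 1.3%.
- **The consequence is small.** Aim 1 states a prediction; there is no control arm and no go/no-go rule on these criteria, and a reader given the session and attrition figures could apply either cut-off. The 20% in section C2 is a recruitment allowance, not a threshold. All of this limits the harm to the reported conclusion. It does not say which conclusion the investigators should report.

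**Conclusion.** The concern holds. The lowest count allowed for each Aim 1 criterion fails the strict percentage it restates, by one session and one firefighter, and no section reconciles them. That part is exact and needs no assumption beyond judging sessions per participant out of 20, as the count form implies.

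The practical size does rest on assumptions. With independent retention between 75% and 90%, the two forms of the retention criterion disagree with probability between 9.0% and 21.8%, the highest of the rates examined being at the planned 80%. The effect is on the stated feasibility and acceptability conclusion for the primary outcomes. It should be fixed before the Aim 1 data are analysed.

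**What to change.** Use one rule, worded identically in section A (Aim 1) and section C4. Either would do:

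- **Option A:** change the percentages to at least 75% of sessions and at most 20% attrition, and keep 15 of 20 sessions and 16 of 20 firefighters.
- **Option B:** keep more than 75% and less than 20%, and change the counts to 16 of 20 sessions and 17 of 20 firefighters.

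Under either option, state that the 75% is judged for each participant out of 20 sessions. If the sponsor prefers a percentage pooled over all enrolled, remove the counts, because they are not equivalent to it.

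The cost is wording in two sections, with no change to conduct. Option A loosens the stated percentages to admit the boundary. Option B makes the criterion one session and one firefighter harder than the stated counts.

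### Aim 1 gives feasibility and acceptability separate percentages and then one joint count, without defining the percentages or saying which form decides; on a pooled reading the two forms can disagree

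*Combined protocol and SAP*

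**What the plan says.** The criterion appears twice, with slightly different force.

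- **Section A, Aim 1.** The prediction is that "CES is feasible quantified as more than 75% of sessions completed, and acceptable quantified as less than 20% attrition in the sample", continued as "such that at least 16 out of 20 firefighters complete, for example, at least 15 out of 20 sessions over the course of four weeks". Here the 15 of 20 is offered only as an example.
- **Section C4.** The main goals are "assessing feasibility (i.e., > 75% of CES sessions completed") and "acceptability (i.e., < 20% attrition in the sample"), followed by the restatement "at least 16 out of 20 firefighters complete at least 15 out of 20 sessions over four weeks". Here the 15 of 20 is no longer an example.

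C4 then names two separate primary outcomes: "number of completed sessions to quantify feasibility and attrition in the sample assessing acceptability (Aim 1"). Section C2 recruits 20 on an estimated 20% attrition so as to have data on 16.

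Four things are not stated in either place: whether the 75% is a share of all sessions in the sample or a share for each firefighter; whether attrition means withdrawal, a missed Visit 4 or too few sessions; whether people who leave stay in the session denominator; and which form decides if the two disagree.

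**The concern.** A percentage of sessions, if pooled, is a total over the sample and can be carried by the most adherent members. Attrition is about leaving. The count asks something else: how many individuals reached a personal minimum. Joining them with a restating phrase treats them as one rule. If they are not, the answer to the primary question depends on which form is applied, and that choice could be made after the data are seen.

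The count also gives one verdict for two questions. A firefighter who attends every visit but does 14 sessions is scored the same as one who withdraws in week one. CES is meant for off-duty days and has to fit around shift work, so staying in the study while missing sessions is a plausible outcome. A future trial would respond to it differently from withdrawal.

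**Working it through.** **Inputs.** 20 firefighters (C1, C2); at most 20 sessions each (Aim 1, C4, and the payment cap in section D), so 20 × 20 = 400 sessions; cut-offs > 75% and < 20%; count rule of at least 16 people with at least 15 sessions. The plan gives no error rate, power or variance for Aim 1.

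**Reproducing the plan's figures.** 0.75 × 20 = 15 sessions; (1 − 0.20) × 20 = 16 firefighters; 16 / (1 − 0.20) = 20 recruited. The counts are therefore the percentages applied to 20, taken at equality. Read strictly, more than 75% of 20 needs 16 sessions (80%), and less than 20% of 20 allows at most 3 losses (15%). Data exactly at the count minimum (15/20 and 16/20) fail both strict percentages.

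**Reading 1: 75% per firefighter, attrition meaning not reaching it.** The percentages and the count are one rule apart from that boundary mismatch.

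**Reading 2: 75% pooled, attrition meaning leaving.** The forms separate:

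| Pattern | Pooled sessions | Attrition | Firefighters with ≥ 15 |
|---|---|---|---|
| 10 do 20, 10 do 11, none leave | (200 + 110)/400 = 77.5%, pass | 0%, pass | 10/20, fail |
| 12 do 20, 8 do 12, none leave | (240 + 96)/400 = 84%, pass | 0%, pass | 12/20, fail |
| 17 do 16, 3 leave with none | 272/400 = 68%, fail | 3/20 = 15%, pass | 17/20, pass |

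The third row turns on the denominator: over the 17 retained it is 272/340 = 80%, a pass.

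**Bounds.** Pooled completion can exceed 75% with as few as 4 people reaching 15 sessions: 4 × 20 + 16 × 14 = 304, or 76%; with 3 it is 60 + 238 = 298, or 74.5%. The count can be met at 16 × 15 = 240, or 60% of sessions. Both bounds lie on or beside a cut-off, so they show the range and not a typical case.

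**Acceptability alone.** In the first two rows nobody leaves, so attrition is 0%. Acceptability fails there only if the joint count is taken to define it. In the other direction, if attrition means leaving before 15 sessions, 16 people reaching 15 leaves at most 4/20 = 20% attrition, so the count can pass against the percentage only at exactly 4.

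**Frequency under assumptions.** Sessions were simulated as beta-binomial for 20 firefighters, with 200,000 trials per setting. None of the adherence or dropout values comes from the plan.

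- Mean completion 80–90%, between-person SD 10–15 points, dropout 5–10% at a uniform time, inclusive cut-offs in both forms: the forms disagree in about 10% to 56% of trials. A re-run with strict percentage cut-offs gave 10.0% to 54.5%.
- No withdrawals, intraclass correlation 0.1–0.3, strict > 75%: pooled passes and the count fails in 42–44% of trials at a true mean of 75%, 56–60% at 80%, 25–39% at 85% and 3–11% at 90%.
- The reverse conflict occurred in under 1% of trials in every setting with dropout, and under 0.1% without.
- In the settings with dropout, 59% to 92% of the disagreements had at least 14 firefighters reaching 15 sessions, mostly one or two short of 16.

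**The case against.** The strongest defence is that there is only one rule. The plan never calls the 75% pooled; in C4 the words about the sample attach to attrition and not to sessions. The linking phrases present the count as the operational form, and the numbers map exactly (75% of 20 is 15, 80% of 20 is 16). On that reading only the boundary mismatch remains.

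This stands in part. A reader might infer that the plan contains two rules that plainly contradict each other; the documents do not support that, because the pooled reading is permitted but not stated. The per-person reading is not stated either. It needs attrition to mean doing too few sessions, which sits badly with C4 naming sessions and attrition as separate outcomes.

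A reader might also infer that the trial could not tell missed sessions from withdrawal. That is not so. Participants log the day, time and duration of each session, staff check in at least weekly, Visit 4 includes a debriefing (C3), and the circumstances of noncompliance and withdrawal are tracked (D3). Only the joint verdict merges the two.

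Finally, this is a 20-person single-arm pilot, Aim 1 is worded as a prediction, and there is no test or go/no-go rule. That lowers the stakes. It does not remove the need for a defined primary criterion, since C4 disclaims power for efficacy and says the 20 participants are there to achieve the listed aims.

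**Conclusion.** The concern holds in limited form. The primary criterion is under-defined, and on one of its two open readings the percentages and the count can give opposite answers, including away from the cut-offs (84% of sessions and 0% attrition against 12/20). The conflict is almost entirely one-way, with the percentages passing and the count failing, so the pooled percentages are the more lenient form. The reverse is rare and depends on whether leavers stay in the denominator.

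The rate of about 10% to 56% depends on assumed adherence and dropout and on the pooled reading. It should not be taken as a rate of gross contradiction, since many of the disagreements are one or two firefighters from the cut-off. Tidying the inequalities alone would not settle the point, because the unit, the denominator and the meaning of attrition would still be open.

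This should be fixed. It does not invalidate the trial: both component outcomes are named and the data to report them separately will be collected.

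**What to change.** In Aim 1 and C4, replace the joint restatement with two criteria, each with a pass mark from the plan's own figures.

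1. **Feasibility:** at least 16 of all 20 enrolled firefighters complete at least 15 of 20 sessions. Drop the example wording in Aim 1 and align the strict 75% with this count.
2. **Acceptability:** the proportion of the 20 who leave the study or permanently stop CES, whatever their session count, is below 20%, that is at most 3 of 20. If 4 of 20 is meant to pass, restate the inequality. The choice matters because C2 plans for exactly 20% attrition: 4 early leavers with the other 16 all reaching 15 sessions would pass feasibility and fail a strict acceptability criterion.
3. State that both must be met for Aim 1 to succeed, and report the pooled percentage of sessions over all enrolled as descriptive.

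**Cost.** Wording only; the session logs and withdrawal tracking already supply the data. The per-person criterion is usually harder to meet than a pooled percentage. In the no-withdrawal simulation at an assumed mean completion of 90%, the pooled form passed in 99.9–100% of trials and the count in 88.5–97.5%; at 85% the figures were 97.5–99.8% and 59–75%. The count is already in the plan, so this settles which bar applies and does not add a new one.
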